7.6 Safety Evaluations

Safety and tolerability will be assessed throughout the study by monitoring and evaluating AE including any complications resulting from the intravenous infusion. All TEAE will be collected from the start of study drug administration in the double-blind period of the study through the start of study drug administration in the OLE period of the study, Day 225, if patient is not enrolling in the OLE period of the study, or 84 days after last dose, if ET.

Severity will be assessed using the National Cancer Institute (NCI) Common Terminology Criteria for Adverse Events (CTCAE), version 5.0 or most current version. All AE will be assigned a severity grade and will be assessed for clinical significance and relationship to study drug. Adverse events of special interest will be noted.

Additional safety evaluations include clinical laboratory tests comprising ADA to AK002, CBC, chemistries and urinalyses, physical exams, and vital sign measurements.

The Medical Monitor will review blinded safety data throughout the study. Certain safety data (post-treatment cell differentials, as well as tissue eosinophil and CCI [REDACTED]) will not be provided to study sites or to the Sponsor as it may cause bias. The designated Safety Monitor will review blinded safety data as well as post-treatment cell counts and will escalate to the Medical Monitor as needed in a manner that does not cause bias.

An independent Data Monitoring Committee (iDMC) has been convened and will meet at regularly scheduled intervals in accordance with the iDMC charter.

8. Prior and Concurrent Medications

Prior and concomitant medications include both prescribed and over-the-counter medications and will be recorded in the electronic Case Report Forms (eCRF) for 30 days prior to the screening visit. Prior medications used for the treatment of EoD symptoms, even if they are >30 days before the screening visit, will be documented in the eCRF.

For patients participating in the OLE period, concomitant medications should be recorded in the AK002-021 double-blind treatment period database beginning after the first administration of study drug in the double-blind period of the study up until the first open-label dose is administered after the Day 176 visit. This includes the prednisone premedication administered after the Day 176 visit in the OLE period, which should be recorded in the Concomitant Medications CRF of both the AK002-021 double-blind treatment period database and the AK002-021 OLE period database.

Any medications should have been stopped as required in the exclusion criteria. Patients should be advised against taking any new medication, both prescribed and over the counter, without consulting the Investigator, unless the new medication is required for emergency use or it is a vaccine to prevent COVID-19. Immediately prior to the first infusion, study site personnel should ensure that the patient continues to meet the inclusion criteria and none of the exclusion criteria (including no receipt or use of prohibited medications).

All medications taken for the 30 days before screening and during participation in this study must be documented on the eCRF. All medications used to treat IRR or AE must be documented. All medications given as preparation for and during the conduct of the EGD and colonoscopy must also be documented.

All AE, whether elicited by questions from study staff, volunteered, or noted on physical examination/laboratory testing, and regardless of causality or severity, will be assessed and recorded in the eCRF beginning after the first administration of study drug in the double-blind period of the study and ending at the time of study completion or early termination of the double-blind period or the OLE period, whichever is later.

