11.3 Safety-Related Procedures

11.3.1 Concomitant Medications

All concomitant medication and concurrent therapies will be documented at screening and at study visits if changes are made. Dose, route, unit, frequency of administration, indication for administration, and dates of medication will be captured. Any prior medication received within 30 days before screening and during the study through Day 225 (± 3) or 84 (± 3) days after last dose of study drug, if ET, will be recorded, or through the first dose of study drug if patient enters the OLE period of the study. Any medications taken for EoD or EoD-related symptoms at any time (even if longer than 30 days before screening) should be listed as concomitant medications, even if the medications were discontinued prior to study participation.

For patients participating in the OLE period, concomitant medications should be recorded in the AK002-021 treatment period database up until the first open-label dose is administered after the Day 176 visit. This includes the prednisone premedication administered prior to the first dose administration visit in the OLE period, which should be recorded in the Concomitant Medications CRF of both the AK002-021 treatment period database and the AK002-021 OLE period database. Rescue medications and procedures must be documented as rescue treatment in the source documents and on the Prior and Concomitant Medications eCRF.

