19.13 Appendix 13: Open-Label Extension Period – Optional

19.13.1 Summary of the Open-Label Extended Dosing Period

Patients who receive all 6 infusions of study drug (AK002 or placebo), complete study visits through Day 176 (± 3) of the double-blind treatment period and meet extended dosing eligibility criteria will be given the option to receive 6 doses of AK002 through the Open-Label Extended Dosing (OLE) period.

Patients will follow the visits and procedures of the double-blind period of the study until starting the OLE period of the study. At least 1 day after Day 176 (± 3), eligible patients participating in the OLE period will begin following the OLE Schedule of Assessments ([Table 8](#)) and will no longer follow the double-blind period of the study Schedule of Assessments ([Table 2](#)). It is important that the first dose of the OLE period is started *after* Day 176 to allow the patient to receive prednisone premedication 12–24 hours prior to the first dose of AK002 in the OLE period. The extended dosing period is summarized as follows:

- The Investigator will evaluate whether the patient is eligible for OLE. If eligible, the patient will be given the option to participate in the OLE period and receive 6 doses of open-label AK002.
- On OLE Dose 1, eligible patients who completed all double-blind Day 176 required procedures will be instructed to begin following the OLE Schedule of Assessments ([Table 8](#)).
- All patients will receive 80 mg oral prednisone 12–24 hours prior to the first infusion in the OLE period. An approved alternative(s) may be used with the approval of the Medical Monitor. Premedication may be administered prior to subsequent infusions at the Investigator's discretion, but only with written approval from the Medical Monitor.
- OLE patients will receive 6 doses of open-label AK002 (OLE Days 1, 29, 57, 85, 113, and 141). All open-label AK002 infusions will be given at a dose of 3 mg/kg.
- Patients will remain at the site for at least 1 hour of observation after each dose. In the event of an IRR, the patient may require prolonged observation (>1 hour or until the symptoms resolve) as per the Investigator's discretion.
- Patients will be followed for approximately 8 weeks after last dose. Follow-up visits will occur on Day 344 (± 7) and Day 372 (± 7) (OLE Day 169 and OLE Day 197, respectively).

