- 30) The ET visits should be conducted 28, 35, 56, and 84 ( $\pm 3$ ) days after last dose of study drug or prior to this, if necessary, to ensure compliance with the visit. If only 1 ET visit is possible, EGD + colonoscopy and end-of-study procedures may occur on the same day. If the end-of-study visit occurs more than 35 days after last dose of study drug, then perform the visit as soon as possible. The procedures listed under the 28-day and 35-day post-study drug visit will be conducted unless otherwise directed by the Medical Monitor. For patients participating in the OLE period, AE and concomitant medications should be collected and recorded in the AK002-021 double-blind treatment period database up until the start of the first open-label infusion after the Day 176 visit. This includes prednisone premedication administered after the Day 176 visit of the OLE period, which should be recorded in the Concomitant Medications CRF of both the AK002-021 double-blind treatment period database and the AK002-021 OLE period database.
- 31) The final hematology assessment for the double-blind period of the study **must** be collected **prior to** the patient taking prednisone premedication for the first dose of the OLE period. Therefore, dosing in OLE must take place at least 1 day after completion of the Day 176.
- 32) Stool antigen test for *H. pylori* will be obtained to confirm no existing active *H. pylori* infection is present. Fecal collection fecal kits (same container as for ova and parasite testing) should be returned to the clinical site within 1 day of collection. Negative results must be available prior to randomization. If *H. pylori* is detected in tissue biopsies by the central pathologist, the patient should be excluded from the trial. In case of a positive test, the patient must be screen failed. After *H. pylori* treatment and an additional 6 weeks later, patient may be reconsented and will receive a new patient number.

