#### 5.4.3 Missing or Partial Dates of Adverse Events or Concomitant Medications

Adverse events with incomplete start or stop dates (i.e., either day or month is missing) will be considered treatment-emergent adverse events (TEAE) unless the partial start date or the stop date confirms the AE started or ended prior to Study Day 1 (e.g., the day of the AE start date is unknown but the month and year indicate that the AE starts prior to Study Day 1). Adverse

events with missing relationship to study drug will be included in the “Related” category for the summary tables and footnoted. Adverse events with missing severity will not be included in the by-severity summary table but will be footnoted in the table.

When there is incomplete information regarding dosing dates for prior and concomitant medication, the medication will be considered as a concomitant medication unless it contradicts with the stop date. For example, a medication will be considered a prior medication if the month and year of the end date indicates a date before Study Day 1 even though the start date could be missing.

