### **6.10.2 Prior, Concomitant, and Newly Initiated Medications**

Prior medications and concomitant medications will be extracted from the Prior/Concomitant Medication CRF. Medications taken prior to Study Day 1 will be considered as prior medications; medications taken on or after Study Day 1 will be considered as concomitant medications; and newly initiated medication refers to any medication with a start date  $\geq$  Study Day 1. We note that a Prior Medication may also be a Concomitant Medication if the start date is prior to Study Day 1 and the end date is on/after Study Day 1. Medications will be coded using the WHO Drug Dictionary (WHODD March 2018 release) for PT and Anatomical Therapeutic Chemical (ATC) classification.

Medications will be tabulated separately based on the Safety population. The number (n and %) of subjects taking at least 1 medication and the number (%) of subjects taking each medication at

the preferred term level will be tabulated by ATC4, and PT. Subjects taking the same PT medication twice will only be counted once.

A subject data listing will be provided to include the reported medication name, the WHODD PT, ATC4, study day and pertinent subject information. A separate data listing will include subjects who have received prohibited medications.

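### Extension-period prednisone premedication is counted in the double-blind concomitant-medication table, so its prednisone row largely measures who entered the extension

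*Protocol*

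**What the plan says.** **Recording.** Concomitant medications for extension patients go into the double-blind database until the first open-label dose. Protocol Section 8 adds "This includes the prednisone premedication administered after the Day 176 visit in the OLE period". It has that dose entered twice, once on the medication form of each period's database. Protocol 11.3.1, Table 2 note 30, Appendix 13 (19.13.4) and Table 8 note 15 give the same instruction. The SAP repeats it in Table 1 note 30: "This includes prednisone premedication administered after the Day 176 visit of the OLE period".

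**Who takes it.** Appendix 13 (19.13.1) says: "All patients will receive 80 mg oral prednisone 12–24 hours prior to the first infusion in the OLE period". This covers entrants from both randomised arms. The Medical Monitor may approve an alternative.

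**Classification.** SAP Table 2 calls a CRF entry concomitant if its end date is on or after Study Day 1, and newly initiated if its start date is on or after Study Day 1. SAP 6.10.2 says "medications taken on or after Study Day 1 will be considered as concomitant medications". Neither place gives a last date.

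**Counting.** SAP 6.10.2 tabulates subjects by ATC level 4 and preferred term in the Safety population, with the rule "Subjects taking the same PT medication twice will only be counted once". The planned output is Table 14.1.8.2 in SAP Appendix 3.

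**The concern.** Each rule is reasonable alone, but together they saturate one row. Every entrant who takes the extension premedication is counted in the prednisone row of a table meant to describe the double-blind period. A patient who also took prednisone during that period, as rescue, for an infusion reaction or as approved premedication before a later infusion, adds nothing further.

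Table 14.1.8.2 is the only between-arm table of concomitant medication in SAP Appendix 3. Its reader would see high prednisone use in both arms and little difference between them, whatever happened on treatment. If extension uptake differs by arm, that imbalance would show up as a difference in prednisone use.

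**Working it through.** The documents give no figure to reproduce, so the check has two parts: the rules in sequence, then the size of the effect.

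**Rules in sequence**

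1. The premedication is taken after the Day 176 visit and 12–24 hours before the first open-label infusion, so its dates fall after Study Day 1. By SAP Table 2 it is both concomitant and newly initiated.
2. It sits in the double-blind CRF by instruction, and no SAP text removes or flags it.
3. The mandatory dose before the first double-blind infusion does not already fill the row. Protocol 7.1 places it on the day before that infusion, so by date it is a prior medication. Without the extension entry the prednisone row would carry information.
4. Week 24 ends on Day 24 × 7 = 168. The earliest Day 176 visit under the ±3 window is Day 173. The premedication therefore falls after the Weeks 23–24 symptom data and outside the Week 21–24 steroid window in SAP Appendix 2.

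**Size**

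Inputs:
- p = true share of an arm taking prednisone during the double-blind period, on or after Day 1. Not given. Assumed 25% in one arm and 5% in the other.
- f = share of the remaining patients who enter the extension and take prednisone for it. Not given for this trial. Protocol 2.3 reports that more than 90% continued into the Phase 2 extension study. The range 0.5 to 0.9 is shown.

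A patient is absent from the row only by being neither a true user nor an entrant, so

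displayed share = 1 − (1 − p)(1 − f).

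With f equal in both arms,

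displayed difference = (1 − f) × true difference.

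Whether the true users themselves enter does not matter, because they are already counted.

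| f | Arm with p = 25% | Arm with p = 5% | Displayed difference | True difference |
|---|---|---|---|---|
| 0.5 | 1 − 0.75 × 0.5 = 62.5% | 1 − 0.95 × 0.5 = 52.5% | 10 points | 20 points |
| 0.8 | 1 − 0.75 × 0.2 = 85.0% | 1 − 0.95 × 0.2 = 81.0% | 4 points | 20 points |
| 0.9 | 1 − 0.75 × 0.1 = 92.5% | 1 − 0.95 × 0.1 = 90.5% | 2 points | 20 points |

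If f differs by arm, the row can mislead in direction as well. With f = 0.8 in the 25% arm and 0.9 in the 5% arm, it reads 85.0% versus 90.5%.

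With the premedication excluded, the row shows p itself: 25% versus 5%.

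**The case against.** **Nothing is lost.** A reader might infer that true double-blind prednisone use is hidden. The documents do not support that. SAP 6.10.2 plans a by-subject listing with study day and a separate prohibited-medication listing. SAP 6.11 plans an intercurrent-event listing with dates and a summary by arm. Protocol 11.3.1 has indication and dates captured and rescue marked as rescue. This stands, and it limits the point to a summary table. It does not remove the point. Listings give no arm-level rates, and for doses above 10 mg/day the intercurrent-event summary counts only Weeks 21–24 and leaves out infusion prophylaxis and reaction treatment.

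**The safety endpoint is not undermined.** A reader might tie this to the endpoint of medication changes due to adverse events. The link is loose. Table 14.1.8.2 counts use for any cause and would not isolate that endpoint even if corrected. Medication given for an adverse event is recorded as an action taken (Protocol 13.6.5), and SAP 6.15.1 lists that action.

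**Other steroids are not masked.** A corticosteroid coded to another preferred term keeps its own row. This stands.

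**The size is assumed.** Entry requires all six infusions and the Day 176 visit, and it is barred if the drug was poorly tolerated. Uptake could fall below the Phase 2 figure, and at f = 0.5 half of the gap remains. This is why a range is shown.

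**Long-stopped drugs appearing as current.** Protocol 11.3.1 says that past EoD drugs "should be listed as concomitant medications, even if the medications were discontinued prior to study participation", and SAP 5.4.3 says of incompletely dated drugs that "the medication will be considered as a concomitant medication unless it contradicts with the stop date". A reader might infer that old steroids or immunosuppressants would be tabulated as on-study use. But the SAP classifies by date and not by CRF label, Protocol Section 8 calls these drugs prior medications, and SAP 5.4.3 lets a month and year of stopping before Day 1 settle the matter. What remains is a conservative default for drugs with no usable stop date, which is not part of this point.

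**Conclusion.** The point holds as a reporting defect of limited reach. Followed as written, the plan makes the prednisone row of Table 14.1.8.2, the subtotals that contain it, and any newly initiated summary largely a count of extension entrants. The true arm difference shrinks by the factor (1 − f): to half at f = 0.5, a fifth at f = 0.8 and a tenth at f = 0.9.

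This rests on three assumptions: uptake among non-users is equal in both arms, nearly all entrants take prednisone and not an approved alternative, and the 25% and 5% are illustrative. Actual uptake and use are not in the documents, so near-universal prednisone use in the table is a conditional result. The dated listings, the intercurrent-event outputs and the co-primary analyses are unaffected.

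**What to change.** Add one rule to SAP 6.10.2: medication recorded as premedication for the first open-label infusion is excluded from the double-blind concomitant and newly initiated summaries, or shown there in a separate labelled row, and is kept in the by-subject listings and the extension tables. The date and indication already collected are enough to identify it.

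Keep the dual recording. Protocol 13.1 and Table 2 note 28 record adverse events in the double-blind database until the first open-label infusion starts, and this prednisone is taken before that. Moving it to the extension database alone would separate a steroid exposure from events recorded in the same interval.

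The cost is one added programming rule. No new data are needed, and no clinical procedure changes.

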8.1 Prohibited Medications

Any biologics or other medications, such as systemic immunosuppressive or immunomodulatory drugs that may interfere with the study efficacy or safety assessments including but not limited to IL-5 modulators (e.g., benralizumab, reslizumab, mepolizumab), IL-4 and/or IL-13 antagonists (e.g., dupilumab), calcineurin inhibitors (e.g., cyclosporin, tacrolimus), mTOR inhibitors (e.g., sirolimus, everolimus), anti-metabolites (e.g., azathioprine, methotrexate, 6-mercaptopurine, leflunomide, mycophenolate mofetil), alkylating agents (e.g., cyclophosphamide), TNF inhibitors (e.g., infliximab, adalimumab), anti-IgE antibodies (e.g., omalizumab), JAK inhibitors, and eosinophil-depleting drugs (e.g., pramipexole).

Patients will be reminded to not take prohibited medications and to notify the site immediately if a prohibited medication is prescribed by another health care provider. If a prohibited medication is started during the course of the study, the patient may be withdrawn from study treatment and followed for the 12-week follow-up period. The follow-up EGD may not be performed.

Vaccination with live attenuated vaccines within 30 days prior to initiation of treatment in the protocol, during the treatment period, or vaccination expected within 5 half-lives (4 months) of AK002 administration is prohibited.

Prohibited medication(s) given within 24 hours of an infusion, if medically necessary for the treatment of an IRR, is acceptable and not considered a deviation from the protocol.

8.2 Restricted Medications

The use of systemic corticosteroids given as pre-infusion prophylaxis or for the treatment of IRR is allowed and will not be considered a deviation from the protocol. The use of systemic or swallowed corticosteroids at a dose equivalent to >10 mg/day of prednisone for the treatment of EoD at any point in the study will be considered rescue therapy. However, the subject may remain in the study. The use of systemic or swallowed corticosteroids at a dose equivalent to >10 mg/day of prednisone is restricted and must be limited to cases of medical necessity when no other alternatives are available. The corticosteroids must be documented along with the reasons for use, and attempts should be made to discontinue the corticosteroids as early as possible.

The use of PPI during the study is allowed provided that the subject is on a stable dose during the screening period and agrees to continue on the same dose through the end of the study. Initiation of PPI therapy or an increase in the dose of an oral PPI following the screening period will be considered a rescue therapy and will only be allowed if the Investigator deems such treatment to be medically necessary. In this case, discontinuation of the PPI therapy prior to Study Week 21 should be considered if medically safe in the opinion of the Investigator.

The use of sodium cromolyn for subjects who were on a stable dose during the screening period is allowed provided that they are willing to remain on the same dose of sodium cromolyn through the end of the study. Initiation or increase in the dose of sodium cromolyn following the screening period will be considered a rescue therapy and will only be allowed if the Investigator deems such treatment to be medically necessary. In this case, discontinuation of the sodium cromolyn therapy prior to Study Week 21 should be considered if medically safe in the opinion of the Investigator.

8.3 Allowed Medications

Medications, other than those that are prohibited or restricted (Section 8.1 and Section 8.2), such as antihistamines, leukotriene antagonists, and sodium cromolyn are allowed during the study and, unless required due to unforeseen medical necessity, doses and/or dietary modifications are to remain stable.

All types and formulations of vaccines approved by FDA or other regulatory authority for the prevention of COVID-19 may be administered before, during, or after the study. The vaccine should not be administered within 7 days before and within 7 days after the administration of study drug so that any side effects caused by either of the 2 medications can be more easily determined.

Systemic or swallowed corticosteroids with a dose of ≤ 10 mg/day prednisone or equivalent being used at the time of study entry are acceptable as long as the dose remains stable throughout screening and during the study.

Short courses or a single use of corticosteroid therapy at doses of ≤ 10 mg/day of prednisone or equivalent due to unforeseen medical necessity for conditions other than the disease under study will be allowed at the discretion of the Investigator provided that the corticosteroids are discontinued prior to Study Week 21. Consideration should be given to alternative therapies whenever possible.

Swallowed or systemic corticosteroids at a dose of >10 mg are not considered prohibited under the following circumstances:

- Systemic corticosteroids given within 24 hours of the start of an infusion when medically necessary for the treatment of an IRR.
- A single dose of IV corticosteroid given during the EGD to minimize AE associated with anesthesia (e.g., nausea and vomiting after anesthesia).
- Premedication with prednisone prior to Dose 1 in the double-blind period and Dose 1 in the OLE period, as required by the protocol.
- Premedication with a systemic corticosteroid (for any dose other than Dose 1 in the double-blind period and Dose 1 in the OLE period), which has been preapproved by the Medical Monitor prior to dosing.

All medication used during the screening period and throughout the study will be documented in the CRF. Any allowed medications that are taken must remain stable throughout the study.

Medications administered for the EGD and colonoscopy are allowed. Medications administered for bowel preparation prior to colonoscopies are also allowed.

All patients will be pretreated with 80 mg prednisone the day before the first infusion.

9. Study Treatment

